8.3 Secondary effectiveness analysis

No secondary effectiveness data will be collected for this study.

8.4 Analysis of follow-up data

The following follow-up data will be summarized descriptively for 30-day (± 7 days) and 60-day (± 14 days) visits:

- Re-hospitalizations since previous study visits;
- CSF leak or pseudomeningocele determination data;
- Surgical site assessment data;
- Wound healing assessment data;
- Presence of clinically significant changes to subject since previous study visit (for 30-day only);
- Laboratory data (complete blood count with differential, liver function tests and electrolytes) (for 30-day only).

8.5 Statistical/analytical issues

8.5.1 Handling of dropouts or missing data

The analysis for the ITT set will be performed considering missing data as failures; in addition, sensitivity analyses for the ITT set will be performed considering missing data as successes, and, as worst-case, with missing data for the EVICEL[®] group considered as failures and missing data for the DuraSeal[™] group considered as successes.

If there are incomplete dates and calculations (e.g. time since procedure) are needed, the following rules are used (no rules will be applied for missing years; this data would normally be expected to be queried):

- Missing date which includes the procedure data: the rules below are followed unless the derived date is pre-procedure, when the derived date will be 1 day after the procedure.
- Missing day: 15th used

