### **6.4 Concomitant Medications**

#### **6.4.1 Documentation of Concomitant Medications**

Indication and start-stop dates of concomitant medications administered from 24 hours prior to surgery up to the 60-day follow-up visit will be recorded. This will include medications that subjects are using chronically.

Anesthetics used for the study surgery and over the counter (OTC) drugs will not be recorded as concomitant medication (with the exception of prophylactic aspirin and those administered to treat adverse events, which should be documented). Concomitant medications used to treat Adverse Events must also be documented, including OTC medications. Doses and routes of administration are not required to be reported.

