10.3 Listings

Listings will be presented in centre, subject and visit order. The listings will be produced using the data from all subjects.

The columns indicate the listings that will be included in the report. All data available on the database, with the exception of fields used for administration, e.g. signature fields, will be included in the listing for the report.

Missing data will be shown by a space.

10.3.1 Appendix 16.2 listings:

All listings will be prefixed with 16.2.

| No | Title of listing | Notes | CRF Page |
|-----|---|--|---------------------|
| 1 | Disposition of subjects | | |
| 1.1 | Disposition of subjects | Includes reason for withdrawal and time to withdrawal | 46 |
| 1.2 | Visit dates | Includes informed consent and discharge details Includes derived data: -Nights in hospital -Days from procedure | Various |
| 2 | Protocol deviations | | |
| 2 | Protocol deviations | | 44 and 45 |
| 3 | Subjects excluded from the analysis | | |
| 3 | Definition of analysis sets | As defined in Section 5 of this SAP | |
| 4 | Baseline characteristics | | |
| 4.1 | Demographics, special histories, smoking status, pregnancy test and subject eligibility operative procedure, type of approach, indication for surgery, specification of tumor | | 3, 4, 5, 10, and 11 |
| 4.2 | Physical exam / medical / surgical history | | 6, 7, and 8 |
| 4.3 | Inclusion and exclusion criteria | | 2 and 13 |
| 4.4 | Concomitant medications | Derived data: -Days from procedure to start -Duration of Con Med | 39 and 40 |
| 5 | Surgical details | | |
| 5.1 | Surgical procedure - re-operative information, timings including operation room and length of procedure, initial CSF leak determination, and randomization data | Includes derived data: -Time in the operating room -Length of procedure | 14, 15, and 16 |
| 5.2 | Surgical procedure – EVICEL application details | | 17 and 18 |
| 5.3 | Surgical procedure – DuraSeal application details | | 17 and 18 |

| No | Title of listing | Notes | CRF Page |
|-------|--|--|--|
| 5.4 | Surgical procedure – watertight closure and amount of treatment used | | 19 |
| 5.5 | Surgical procedure – additional treatments / rescue therapy | | 20 and 21 |
| 6 | Effectiveness data | | |
| 6.1 | Effectiveness - primary effectiveness endpoint | | |

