| 6.1 | Primary effectiveness endpoint - Success (no CSF leak during surgery and up to 30-day visit) - PP set and ITT set (sensitivity analysis) | Includes derived data: Missing data considered as: -Analysis#1: failures (d) Sensitivity analysis - missing data considered as: -Analysis#2: successes (d); -Analysis#3: failures for EVICEL and successes for DuraSeal (d) | |
| 6.2 | Follow-up assessments | | |
| 6.2.1 | Post-surgery to hospital discharge assessment | | 22, 23, 24, 25, 26, and 27 |
| 6.2.2 | 30-day (± 7 days) and 60-day (± 14 days) follow-up assessments | | 28, 29, 30, 31, 32, 33, 34, 35, and 36 |
| 7 | Safety data | | |
| 7.1 | Adverse event listings (each subject) | | |
| 7.1.1 | Adverse events | Includes derived data: -Days from procedure to start -Duration of AE | 42 and 43 |
| 7.1.2 | Adverse event comments | | 43 |
| 7.1.3 | Adverse events (MedDRA codes) | | 42 and 43 |
| 7.1.4 | Serious adverse events | | 42 and 43 |
| 7.2 | Laboratory data | | |
| 7.2.1 | Laboratory data - Complete Blood Count | At baseline, within 72 hours prior to hospital discharge, and at 30-day follow-up | 37 and 38 |
| 7.2.2 | Laboratory data - White Blood Cell Differential | At baseline, within 72 hours prior to hospital discharge, and at 30-day follow-up | 37 and 38 |
| 7.2.3 | Laboratory data – Liver Function Tests and Electrolytes | At baseline, within 72 hours prior to hospital discharge, and at 30-day follow-up | 37 and 38 |
| 7.3 | Other safety data | | |

| No | Title of listing | Notes | CRF Page |
|-----|-------------------|---|--|
| 7.3 | Other safety data | Includes derived data: -Incidence of intra-operative CSF leakage following final Valsalva maneuver; -Incidence of post-operative CSF leakage within 30 days (± 7) post-operatively; -Incidence of post-operative CSF leakage within 60 (± 14) days post-operatively; -Incidence of surgical site infections (SSI) according to NNIS definition and CDC classification within 30 days (± 7) post-operatively | 17, 18, 19, 23, 24, 31, 32, 35, and 36 |

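### SAP 8.5.1 sets every missing day to the 15th for start and stop dates alike, so the listings can show adverse events and drugs that end before they start, and pre-operative drugs dated on or after surgery

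*SAP*

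**What the plan says.** SAP 8.5.1 applies its date rules "If there are incomplete dates and calculations (e.g. time since procedure) are needed". One imputation line follows: "Missing day: 15th used". One bound accompanies it, introduced by the phrase "Missing date which includes the procedure data": the rule holds "unless the derived date is pre-procedure, when the derived date will be 1 day after the procedure". Nothing separates start dates from stop dates, and nothing requires a stop to fall on or after its start.

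The SAP then names calculations that use such dates. In section 10.3.1, Listing 16.2.7.1.1 (adverse events) "Includes derived data: -Days from procedure to start -Duration of AE". Listing 16.2.4.4 (concomitant medications) has the note "Derived data: -Days from procedure to start -Duration of Con Med".

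Protocol 6.4.1 says that "concomitant medications administered from 24 hours prior to surgery up to the 60-day follow-up visit will be recorded", with start and stop dates, and that long-term medication is included. Drugs begun before surgery are therefore expected in the data.

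**The concern.** A mid-month value is a fair guess for a single date standing alone. It is a poor one when the record holds a second, complete date, because the 15th can fall on the wrong side of it. The floor adds a second difficulty. It suits adverse events, which are collected only from randomization onwards, but it is worded for dates in general. Applied to a drug that the patient was already taking, it reverses the order of drug and operation.

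At stake is whether two listings in the study report can be believed. Negative durations are impossible values. A drug wrongly shown as begun after surgery misleads anyone reading the listing to see whether a drug preceded an event.

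**Working it through.** The date rule states no figure to reproduce, so the check applies it literally.

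**Single records**

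- Operation 10 March, event starts 20 March, stop recorded only as March. Derived stop is 15 March; duration 15 − 20 = −5 days.
- Operation 20 March, event starts 24 March, stop recorded only as March. The 15th precedes the operation, so the stop becomes 21 March; duration 21 − 24 = −3 days.
- Operation 20 March, drug begun 2 March but recorded only as March. Derived start is 21 March, Day +1. If the drug was stopped on 20 March, its duration is 20 − 21 = −1 day.

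**How often durations turn negative, per record with one incomplete date**

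Let m be the number of days in the month and L the true duration (stop minus start).

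- Stop day missing: ignoring the floor, the derived stop precedes the start when the start falls on day 16 to day m − L. That is max(0, m − 15 − L) days in the month. A 365-day year has seven months of 31 days, four of 30 and one of 28. For L = 3: (7×13 + 4×12 + 10)/365 = 149/365 = 40.8%. For L = 7: (7×9 + 4×8 + 6)/365 = 101/365 = 27.7%. For L = 14: (7×2 + 4×1 + 0)/365 = 18/365 = 4.9%. For L = 30: 0.
- Start day missing: the derived start follows the stop when the start falls on day 14 − L or earlier. For L = 3: 12×11/365 = 36.2%. For L = 7: 12×7/365 = 23.0%. For L = 14 or 30: 0.

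Full enumeration, floor included, over all 365 operation dates and event starts on Days 0 to 60:

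| True duration | Stop day missing | Start day missing |
|---|---|---|
| 3 days | 39.5% | 36.2% |
| 7 days | 26.8% | 23.0% |
| 14 days | 4.8% | 0% |
| 30 days | 0% | 0% |

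The floor lowers the stop-missing figures slightly, because it rescues events that start on the day of a late-month operation or the day after. If both days are missing within one month, both dates take the same value and the duration is 0. The same counting applies to short drug courses given after surgery.

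**Drugs begun before surgery, in the month of surgery, with no start day**

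Let the operation fall on day p.

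- p < 15: derived start is the 15th, after surgery.
- p = 15: derived start is the day of surgery.
- p > 15: derived start is p + 1, after surgery.

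No case stays pre-operative. The possible pairs of operation day and earlier start day number 7×465 + 4×435 + 378 = 5,373, of which 12×14 = 168 have p = 15. So 168/5,373 = 3.1% land on Day 0 and 96.9% after surgery.

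For starts in earlier months the result depends on how the phrase introducing the floor is read. If the floor covers only partial dates in the procedure month, none of the starts 31 to 365 days before surgery is moved. If it covers every partial date, all of them become post-operative.

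**Which outputs use these values**

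Days to start and duration for adverse events and drugs are named only in Listings 16.2.7.1.1 and 16.2.4.4. The table list in SAP 10.2.2 has no table of event duration, event onset time or concomitant medication. Its adverse-event tables summarise subjects by coded term.

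**The case against.** The strongest reply is that little depends on these values. They appear in listings, safety is descriptive with no inferential analysis (Protocol 8.4.2, SAP 9.4), and no estimate or conclusion changes. That stands, and it sets the size of the point.

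A second reply is that the percentages rest on assumed dates and durations, and that the documents do not say how often a day is missing. That also stands: the rates describe affected records, not the trial. Long events are untouched.

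A third reply is that edit checks, queries and listing review (Protocol 10.3.3, SAP 10.3.2) would catch such records. They may well reduce the number of partial dates. But the negative value arises in the derivation, after data entry, so a record still lacking its day will produce it.

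A reader might go further and infer that the rule can put a leak on the wrong side of the 30-day window, and so move a success rate. The arithmetic allows a shift of −16 to +14 days, but the documents do not support the inference. The SAP's note on changes says the primary endpoint is assessed at the 30-day visit. Table 14.2.1.1 counts success up to that visit, and SAP 8.4 summarises leak determination by visit. Listing 16.2.7.3 takes leak and infection incidence from operative, discharge and follow-up CRF pages, not from adverse-event pages 42 and 43. Nowhere does the SAP say that an imputed onset date decides the window. It is silent on a leak first reported at the 60-day contact; that is a separate question of definition.

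**Conclusion.** The rule is wrong as written, because it produces impossible or reversed values in listings that the SAP itself plans. It is a minor point.

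- Negative durations follow directly from the rule and are concentrated in short events. With the stop day missing they arise in about 40%, 27%, 5% and 0% of affected records at 3, 7, 14 and 30 days. This assumes fixed durations, operation dates uniform over a year and event starts uniform over Days 0 to 60.
- That every drug begun before surgery in the surgery month without a start day is dated on or after surgery needs no distributional assumption. Only the 97% to 3% split between post-operative and Day 0 does. For earlier months the outcome turns on unclear wording.
- The effect is confined to derived days-to-start and duration in Listings 16.2.4.4 and 16.2.7.1.1. The primary endpoint, the tables and the tests are not shown to be affected.

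**What to change.** In SAP 8.5.1, replace the single rule with the following:

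- **Start with missing day:** first of the month. For adverse events, not before the procedure date.
- **Stop with missing day:** last day of the month, capped at the date of last contact.
- **Consistency:** a derived stop may not precede the start, and a derived start may not follow a known stop.
- **Drugs recorded as begun before surgery:** no post-procedure floor. This also removes the doubt about earlier months.

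On the records above, and with last contact after March, the first event then ends on 31 March (31 − 20 = 11 days). The drug starts on 1 March, which is Day −19 for an operation on 20 March. Negative durations cannot occur, by construction.

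The cost is a few lines of SAP text and a small change to the date-derivation code, best made before database lock. The downside is that some durations become slightly longer. No leak-onset rule is needed as part of this change.

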8.5.2 Interim analyses and data monitoring

No interim analysis will be performed for this study.

8.5.3 Multiple comparison / multiplicity

Not applicable.

9. SAFETY EVALUATION

9.1 Adverse events

The following will be summarized using the Safety set:

- Adverse events, collected from time of randomization, throughout the follow-up period until 60 days (± 14) after the procedure;

- Incidence of intra-operative CSF leakage following final Valsalva maneuver;
- Incidence of post-operative CSF leakage within 30 days (± 7) post-operatively;
- Incidence of post-operative CSF leakage within 60 (± 14) days post-operatively;
- Incidence of surgical site infections (SSI) according to NNIS definition and CDC classification within 30 days (± 7) post-operatively;
- Laboratory data (complete blood count with differential, liver function tests and electrolytes).

9.2 Clinical laboratory evaluation

Blood samples will be taken for Complete Blood Count (CBC) with differential, liver tests and electrolytes.

9.3 Vital signs, physical findings and other observations related to safety

Vital signs will not be collected in this study. A physical exam will be performed and medical/surgical history data will be collected at screening.

9.4 Methods of analysis

All safety variables will be summarized descriptively only, for Safety analysis set. No inferential statistical analysis will be carried out.

Adverse events will be summarized descriptively by the treatment received, using Medical Dictionary for Regulatory Activities (MedDRA) terminology, in SI units.

10. DATA PRESENTATION

The report forms part of an integrated clinical study report. The actual numbering of tables, listings and other outputs may change. Numbering is in accordance with ICH guideline E3².

10.1 Procedure or treatment labels

The following labels will be used for all output: **EVICEL** and **DuraSeal**.

10.2 Tables and figures

Data will be tabulated by treatment group and, if appropriate, by visit. Continuous data summaries will present (unless stated otherwise) number of observations, number of missing observations (if there are any), mean, standard deviation, minimum, median and maximum. Categorical data summaries will present the number of observations and the corresponding percentage. The following tables will be produced:

10.2.1 In-text tables and figures

These will be produced for the main report in conjunction with the medical writer. These will include, but will not be limited to:

| No | Title of table/figure | Notes |
|----|--|--|
| F1 | Subject disposition | Based on Table 14.1.1.4 |
| T1 | Demographic characteristics – ITT analysis set | Summary of Table 14.1.2.1 |
| T2 | Surgical procedure – ITT analysis set | Summary of key items from Tables 14.1.3.1-14.1.3.7 |
| T3 | Statistical summary for primary effectiveness endpoint – Per-Protocol and ITT analysis sets (including sensitivity analysis summary) | Summary of Tables 14.2.1.1 and 14.2.1.2 |
| T4 | Summary of AEs occurring in >5% of subjects– Safety analysis set | Summary of 14.3.1.3 |

T=Table F=Figure

10.2.2 Section 14 tables

Shell tables shown in Appendix 1, according to the code in the ‘Shell’ column. All table numbers will be prefixed with 14.

| No | Title of table/figure | Notes | Shell ¹ |
|-------|--|---|--------------------|
| 1.1 | Disposition of subjects, analysis sets and protocol deviations | | |
| 1.1.1 | Disposition of subjects by centre – ITT set | Includes number withdrawn – by center | DS |
| 1.1.2 | Enrollment by center – ITT set | By center | E |
| 1.1.3 | Summary of protocol deviations – ITT set | Includes both minor and major protocol deviations | PD |
| 1.1.4 | Analysis sets – ITT set | | ST |
| 1.2 | Baseline data | Excludes baseline data that is also measured post procedure and/or safety data | |
| 1.2.1 | Demographics – ITT set | Age, height, weight, BMI – continuous data (c); gender, race, ethnicity, history of SVT, DVT/PE, family history of DVT/PE, history of alcohol abuse, smoking status – all discrete data (d) | DG |
| 1.2.2 | Baseline characteristics – ITT set | Presence of relevant history of prior surgery, type of pregnancy test done prior to procedure, indication of any relevant changes in medical history between screening and 24 hours before procedure, and confirmation of subject eligibility (all d) | G1 ² |
| 1.2.3 | Physical exam / medical / surgical history – ITT set | Includes frequencies | HX |
| 1.3 | Operative data | | |

¹ Shell: Example table from Appendix 1 (Shell tables). Letters refer to standard output, numbers to project specific output.

² For Tables G1, G2, G3 notes will indicate if data is continuous or discrete.

| No | Title of table/figure | Notes | Shell ¹ |
|-------|---|--|--------------------|
| 1.3.1 | Pre-operative data – ITT Set | Operative procedure, type of approach, indication for surgery, tumor type, if applicable, and tumor location (if applicable) (all d) | G2 |
| 1.3.2 | Operative data: initial CSF leak determination and randomization data – ITT set | Indication of spontaneous CSF leak observation, indication of Valsalva maneuver performed prior to randomization (if no leak), indication of CSF leak detection after Valsalva (if no leak), specification of treatment to which subject is randomized, and indication of tissue based patch use during primary sutured dural closure – all (d) | G2 |
| 1.3.3 | Operative data: EVICEL application – ITT set | For patients treated with EVICEL, the following data will be analyzed for first EVICEL application and second treatment of EVICEL (if applicable): method of EVICEL application (standard tip, spray or drip, if applicable, control tip, airless spray tip), number of layers applied, indication of spontaneous leak observation, definition of CSF leak observed (if applicable), indication of Valsalva maneuver performed after randomized treatment application (if applicable), indication of CSF leak detection after Valsalva (if applicable), and definition of leak (if applicable) (all d) | G2 |
| 1.3.4 | Operative data: DuraSeal application – ITT set | For patients treated with Control (DuraSeal), the following data will be analyzed for first DuraSeal application and second treatment of DuraSeal (if applicable): method of DuraSeal application, number of layers applied, indication of spontaneous leak observation, definition of CSF leak observed (if applicable), indication of Valsalva maneuver performed after randomized treatment application (if applicable), indication of CSF leak detection after Valsalva (if applicable), and definition of leak (if applicable) (all d) | G2 |
| 1.3.5 | Operative data: watertight closure and other treatment data – ITT set | Total number of kits used, approximate total amount of randomized treatment used, derived volume per kit (all c), indication of watertight closure after randomized treatment application, indication of additional treatment application, and indication of watertight closure at the end of procedure (all d) | G2 |
| 1.3.6 | Operative data: additional treatments/rescue therapy – ITT set | Indication and specification of additional treatments / rescue therapy applied, such as glues/sealants (EVICEL, DuraSeal, BioGlue, Other), sutures (all d), hemostasis matrices (d) (type (d), width (c), length (c)), antologous (fascia, pericranium, fat, muscle, other), and biologic/non-antologous dural patches (all d) | G2 |
| 1.3.7 | Operative data timings – ITT set | Time in operating room (c), length of procedure (from first incision to closure completion) (c) | G2 |
| 2 | Effectiveness data | | |
| 2.1 | Primary endpoint: success (no CSF leak during surgery and up to 30-day visit) | Includes sensitivity analyses | |

| No | Title of table/figure | Notes | Shell ¹ |
|-------|---|--|--------------------|
| 2.1.1 | Success (no CSF leak during surgery and up to 30-day visit): primary effectiveness analysis – PP set | Discrete data | G2 |
| 2.1.2 | Success (no CSF leak during surgery and up to 30-day visit): sensitivity analysis – ITT set | Missing data considered as: -Analysis#1: failures (d) Sensitivity analysis - missing data considered as: -Analysis#2: successes (d); -Analysis#3: failures for EVICEL and successes for DuraSeal (d) | G2 |
| 2.2 | Follow-up assessments | | |
| 2.2.1 | Post-surgery to hospital discharge assessment – ITT set | Presence of clinically significant changes to the subject, CSF leak and pseudomeningocele determination, along with the identification of the test used for diagnosis, surgical site assessment, including presence of infection (brain abscess, meningitis, and/or surgical site infection – superficial incisional, deep incisional and/or organ-space), hematoma (intradural, extradural, and/or subcutaneous), and other surgical site experience, wound healing assessment, indication of subject presence (all d) and duration in ICU (c), and length of subject hospital stay (c) | G2 |
| 2.2.2 | 30-day (± 7 days) and 60-day (± 14 days) follow-up assessments – ITT set | Method of contact with subject, indication of re-hospitalizations since previous study visit, presence of clinically significant changes to subject since previous study visit (for 30-day only), CSF leak and pseudomeningocele determination, along with the identification of the test used for diagnosis, surgical site assessment, including presence of infection (brain abscess, meningitis, and/or surgical site infection – superficial incisional, deep incisional and/or organ-space), hematoma (intradural, extradural, and/or subcutaneous), and other surgical site experience, wound healing assessment (all d) | G2 |
| 3 | Safety data | | |
| 3.1 | Adverse Events | | |
| 3.1.1 | Number of subjects experiencing any during/post treatment AE by category – Safety analysis set | | AS |
| 3.1.2 | Adverse events (during/post treatment) by subject, MedDRA preferred term and system organ class – Safety analysis set | | AM |

| No | Title of table/figure | Notes | Shell ¹ |
|-------|---|--|--------------------|
| 3.1.3 | Summary of during/post treatment adverse events by subject and coded terms, preferred terms occurring in $\geq 5\%$ of subjects – Safety analysis set | | AM |
| 3.1.4 | Summary of during/post treatment serious adverse events by subject and coded terms – Safety analysis set | Includes adverse events for which the answer for CRF question “Serious?” in the CRF is “Yes” | AM |
| 3.1.5 | Summary of during/post treatment surgical procedure related (possibly, definitely) adverse events by subject and coded terms – Safety analysis set | Includes adverse events for which the answer for CRF item “Relationship to surgical procedure” is “Possibly related” or “Related”. | AM |
| 3.1.6 | Summary of during/post treatment study treatment related (possibly, definitely) adverse events by patient and coded terms – Safety analysis set | Includes adverse events for which the answer for CRF item “Relationship to study treatment” is “Possibly related” or “Related”. | AM |
| 3.2 | Laboratory data | Reported in SI units | |
| 3.2.1 | Laboratory data: Complete Blood Count - Safety analysis set | At baseline, within 72 hours prior to hospital discharge, and at 30-day follow-up | L |
| 3.2.2 | Laboratory data: White Blood Cell Differential - Safety analysis set | At baseline, within 72 hours prior to hospital discharge, and at 30-day follow-up | L |
| 3.2.3 | Laboratory data: Liver Function Test and Electrolytes - Safety analysis set | At baseline, within 72 hours prior to hospital discharge, and at 30-day follow-up | L |
| 3.3 | Other safety data | | |
| 3.3 | Other safety data - Safety analysis set | Incidence of intra-operative CSF leakage following final Valsalva maneuver, incidence of post-operative CSF leakage within 30 days (± 7) post-operatively, incidence of post-operative CSF leakage within 60 (± 14) days post-operatively, incidence of surgical site infections (SSI) according to NNIS definition and CDC classification within 30 days (± 7) post-operatively (all d) | G2 |

Note: ‘–’ indicates a new line in the title.

